10.2.4.4 Telephone Visit (Day 134)

Clinic staff will telephone subject to assess safety (AEs) and to record concomitant medications/therapies. Staff will to instruct subject on study drug application, to advise subjects regarding permitted emollient(s) and/or sunscreen for use on nontreatment days (use of

emollient(s) on study drug treatment days within 4 hours of study drug application is prohibited), and to remind subjects that 24 hours must have elapsed since IP application before the subject's next visit. Subjects should not apply IP on visit days until after the visit. An unscheduled clinic visit may be performed, if necessary.

10.2.4.5 Visit 9 (Week 20; Day 150 ±7 days)

The following procedures will be performed at each study clinic visit:

1. Record concomitant medications and concomitant therapies.
2. Record vital signs (blood pressure and pulse).
3. Record IGA.
4. Record VIIS.
5. Record assessment of roughness.
6. Record palm/sole assessment.
7. Record palm/sole assessment of fissuring.
8. Record ectropion score.
9. Assess and record local tolerance/AEs and review diary.
10. Perform a urine pregnancy test for WOCBP.
11. Collect returned study drug tubes; confirm study drug compliance by weighing returned tube contents and reviewing diaries.
12. Weigh new study drug tubes and dispense enough additional study drug until next visit, and new diary.

10.2.4.6 Visit 10 (Week 24; Day 180 ±7 days) or Early Termination

The following procedures will be performed at Week 24 in the study clinic:

1. Perform a physical examination.
2. Record vital signs (blood pressure and pulse).
3. Record concomitant medications and concomitant therapies.
4. Record IGA.
5. Record VIIS.
6. Assess roughness.
7. Record palm/sole assessment.
8. Record palm/sole assessment of fissuring.
9. Record ectropion score.
10. Assess local tolerance
11. Record AEs and review diary.

12. Perform a 12-lead ECG.
13. Perform a urine pregnancy test for WOCBP.
14. Collect blood and urine for routine laboratory tests (subject must be fasting at least 8 hours).
15. Collect a PK blood sample (all subjects)
16. Collect returned study drug tubes; confirm study drug compliance by weighing returned tube contents and reviewing diaries.

10.2.4.7 Follow-up Evaluation – Open-Label Extension (Week 26/Visit 11)

At 14 days after the last administration of the IP, the following procedures will be performed:

1. Perform a physical examination.
2. Record vital signs (blood pressure and pulse).
3. Record any concomitant medications/therapies.
4. Record IGA.
5. Record VIIS.
6. Assess roughness.
7. Record palm/sole assessment.
8. Record palm/sole assessment of fissuring.
9. Record ectropion score.
10. Assess and record AEs occurring since the last evaluation and review diary.
11. Perform a urine pregnancy test for WOCBP.

10.3. Assessments

The 5-point IGA is a valid measure of disease severity and meets the need for a clinically meaningful measure of success for ichthyosis studies. The IGA scale was developed with the support of experts from academic reference centers for the treatment of ichthyosis. Each level of severity will consider both the severity of scaling and the severity of roughness (Section 10.3.1.2). While retinoid treatment is expected to reduce scale, it may increase erythema; therefore, in this study, erythema will be evaluated as part of local tolerability.

10.3.1 Efficacy Variables

All efficacy measurements will use scales previously used for dermatological studies or as defined in the following sections.

10.3.1.1 Investigator’s Global Assessment

The primary endpoint is the number of subjects in each treatment group who experience successful resolution of LI where “success” is defined as clear/almost clear and at least a 2-grade change from Baseline at Week 12/EOT in the Double-blind Period on a 5-point IGA full body scale.

The investigator will rate the subject's condition using the 5-point IGA at each time point shown in the Schedule of Events (Section 2.2).

The IGA will be measured on a 5-point scale, excluding the following areas: knees, elbows, neck, palms, soles, axillae, groin, and scalp:

0	Clear	No scaling and no roughness
1	Almost Clear	Occasional fine scales; hardly palpable roughness (mostly smooth)
2	Mild	Small and fine scales predominate; no more than a few large scales; mild roughness on palpation
3	Moderate	Some large scales that may be thick,; coarse roughness on palpation
4	Severe	Confluent, primarily large (>1 cm), thick scales with plate-like hyperkeratosis

10.3.1.2 Visual Index for Ichthyosis Severity – Scaling

The secondary endpoint is the number of subjects in each treatment group who experience a severity score of 0 or 1 at Week 12/EOT on the overall 16-point VIIS for scaling.

The investigator will rate the subject's condition using the 5-point VIIS for each body area (chest/abdomen, back, legs, and arms) and an overall score at each time point shown in the Schedule of Events (Section 2.2):

0	Normal skin; no perceptible scale or smoothening
1	Areas of normal skin intermixed with areas showing smoothening (diminished fine skin markings; shininess; waxiness) or small scales (visibly separated/fractured stratum corneum)
2	Confluent smoothening (diminished fine skin markings; shininess; waxiness) or small scales (visibly separated/fractured stratum corneum)
3	Confluent scales (visibly separated/fractured stratum corneum) including some large (>1 cm), thick scales
4	Confluent, primarily large, thick scales

10.3.1.3 Individual Score for Roughness

The amount of roughness of the skin overall will be measured on a 5-point scale.

0	Clear	Smooth skin
1	Almost Clear	Hardly palpable roughness
2	Mild	Mild roughness (fine sand paper-like)
3	Moderate	Moderate, coarse roughness (coarse sand paper-like)

- | | | |
|---|--------|---|
| 4 | Severe | Very coarse skin (broken cornflakes-like) |
|---|--------|---|

10.3.1.4 Palm/Sole Assessment

Thickening of the skin on the palms and soles will be measured on a 5-point scale.

- | | | |
|---|--------------|---|
| 0 | Clear | No thickening, no roughness, no fissure |
| 1 | Almost Clear | Only slight thickening, minimal to no roughness, no fissures |
| 2 | Mild | Some thickening, mild roughness on palpation, few fissures may be present |
| 3 | Moderate | Substantial and diffuse thickening, coarse roughness on palpation may be present, fissures may be present |
| 4 | Severe | Very thickened and rough skin, numerous fissures |

10.3.1.5 Palm/Sole Fissuring Assessment

Fissuring will be assessed by recording the presence or absence of fissures, the number of fissures present, and the pain associated with each fissure. A fissure is a longitudinal and deep crack that separates the stratum corneum and may penetrate down to the dermis, causing pain and sometimes bleeding. The subject will assess pain associated with fissures as ranging from 0-3 (none, mild, moderate, severe).

10.3.1.6 Dermatology Life Quality Index

The DLQI is a dermatology-specific Quality of Life instrument for subjects aged 17 years and older (1992). The child DLQI (cDLQI; May 1993) is for subjects aged 12 to 16 years. It is a simple 10-question validated questionnaire with 6 domains (symptoms and feelings, daily activities, leisure, work and school, personal relationships, and treatment); higher scores indicate poorer quality of life. The DLQI is the most frequently used instrument in studies of randomized controlled trials in dermatology. The investigator should use his or her judgment of the maturity of the subject to decide which version of the questionnaire to use; the same version must be used for the subject throughout the study.

10.3.1.7 EQ-5D Quality of Life Questionnaires

The EQ-5D is a standardized instrument developed by the EuroQol Group as a measure of health-related quality of life used in a wide range of health conditions and treatments. The EQ-5D consists of a descriptive system and the EQ visual analog scale (VAS). The EQ-5D-5L (2009) is intended for use in adult subjects, while the EQ-5D-Y (2012) is to be used for children and adolescents. The investigator should use his or her judgment of the maturity of the subject to decide which version of the EQ-5D to use; the same version must be used for the subject throughout the study.

The descriptive system comprises 5 dimensions: mobility, self-care, usual activities, pain/discomfort, and anxiety/depression. The EQ VAS records the subject's self-rated health on a

vertical 0-100 VAS. This can be used as a quantitative measure of health outcome that reflects the subject's own judgement.

10.3.1.8 Ectropion Severity Score

The Ectropion Severity Score (ESS), has a maximum score of 8 points. A higher score indicates a worse ectropion. The score takes the severity of ectropion in terms of lateral and medial apposition, scleral show, conjunctival show, and roundness of the eye into account and gives an indication of the functional aspects involved in ectropion by scoring redness, excess tear film, and the position of the lacrimal punctum.¹⁴

	Points per Item		
	0	0.5	1
Lateral apposition	Nonaffected	—	Affected
Medial apposition	Nonaffected	—	Affected
Scleral show	No	≤1 mm	>1 mm
Conjunctival show	No	—	Yes
Excess tear film	No	—	Yes
Redness of the eye	No	—	Yes
Round canthus	No	—	Yes
Punctum lacrimale	Invisible	Emerging	Visible
Maximum score			8 points

Figure 10-1: Ectropion Severity Score

Source: Korteweg SFS, Stenekes MW, van Zyl FE, Werker PMN. Paralytic Ectropion treatment with lateral periosteal flap canthoplasty and introduction of the ectropion severity score. *Plast Reconstr Surg Glob Open*. 2014;2(5):e151.

10.3.1.9 Photography Substudy

All sites that have photographic capability will take photographs as source data to support scoring at Baseline, Day 30, and Day 90. A central reader who will not be an investigator in the study will review the photographs to assess consistency of investigator scoring of LI severity as a quality check. Photographs may also be used for scientific publication purposes. Subjects will sign a separate, optional photographic informed consent form (ICF).

10.3.2 Clinical Pharmacology

10.3.2.1 Pharmacokinetic Analysis Methods

The pharmacokinetic characterization of drug concentrations for each dose to be profiled will use noncompartmental analysis (NCA).

10.3.2.2 Pharmacokinetic Parameters

Samples for PK will be drawn from all subjects at Baseline and at each clinic visit for trough values.

Subjects who provide written informed consent to participate in the optional PK substudy will provide blood samples for PK analysis predose on Day 1 and at 1, 2, 4, 8, 12, and 24 hours postdose on Day 1 and Day 30.

The PK parameter estimates will be completed using WinNonlin (Pharsight Corporation) software using the actual elapsed times from dose administration to sample collection (i.e., not nominal time).

Standard PK parameters assessed will include measures of the extent of absorption using estimates of the area-under-the-curve (AUC) and rate-of-absorption using the maximum concentration (C_{max}) and the time of C_{max} (T_{max}). Additional details of the parameters and their calculation and evaluation will be included in the statistical analysis plan (SAP).

[Table 10-1](#) shows the PK parameters that will be computed for each subject for samples obtained over the planned sampling intervals.

Table 10-1: Pharmacokinetic Parameters

Parameter	Description of Parameter
C_{max}	Maximum (or peak) serum concentration
T_{max}	Time at which C_{max} is observed
$AUC_{(0-t)}$	Area under the plasma concentration-time curve from time 0 to the time of the last quantifiable plasma concentration
$AUC_{(0-inf)}$	Area under the plasma concentration-time curve from time 0 to infinity (if data permits)
$t_{1/2}$	Apparent first order terminal elimination half-life
λ_z	Apparent terminal phase rate constant (if data permits)

10.3.3 Sample Collection

Samples will be collected at the time points specified in the Schedule of Events (Section 2.2). Specimen preparation, handling, shipment, and storage for the complete blood count, chemistry, and urinalysis are described in the study laboratory manual. Finding veins in subjects with this disease can be challenging. Blood draws will be done at the corresponding study visits before application of the IP and should be 24 hours after IP application. Subjects must not apply the IP to the area where blood will be drawn within 24 hours before their next study visit to avoid contamination of the blood by IP that remained in the skin. For subjects in the PK substudy, a cannula should be placed before IP application and the cannula site may be occluded to prevent contamination with IP.

Actual PK sample times for subjects in the PK substudy will be recorded in the eCRF.

Blood

For subjects not in PK substudy:

The expected amount of blood to be drawn at each visit varies from approximately 6 mL to a maximum of 21 mL (Screening Visit only). The total amount of blood drawn for the study will be about 123 mL per subject, unless the subject takes part in the PK substudy.

For subjects in PK substudy:

For subjects who opt to participate in the PK substudy, extra blood samples will be drawn at Visit 2 and at Visit 4 for PK analysis. The amount of blood to be drawn per subject at each of these visits will be approximately 54 mL. For subjects taking part in the substudy, the total amount of blood drawn for the entire study will be approximately 195 mL.

Urine

Urinalysis will be performed at central laboratory. Dipstick and urine pregnancy tests will be conducted on site.

10.3.4 Safety Variables

Safety assessments will include the evaluation of AEs, including local tolerability (stinging/burning, pruritus, and erythema), clinical laboratory assessments, vital signs, 12-lead ECGs, and physical examinations.

10.3.4.1 Clinical Laboratory Safety Assessments

10.3.4.1.1 Clinical Laboratory Tests to be Performed

Samples for the following laboratory tests will be collected at the time points specified in the Schedule of Events (Section 2.2).

Hematology:	hemoglobin, hematocrit, red blood cell (RBC) count, RBC indices, mean corpuscular hemoglobin, mean corpuscular hemoglobin concentration, platelet count (or estimate), white blood cell count including differential
Serum Chemistry:	albumin, total bilirubin, total protein, calcium, alkaline phosphatase, alanine aminotransferase, aspartate aminotransferase, blood urea nitrogen, creatinine, glucose, sodium, potassium, chloride, bicarbonate, lactate dehydrogenase, uric acid, total cholesterol, high-density lipoprotein, low-density lipoprotein, triglycerides
Coagulation Panel:	prothrombin time, partial thromboplastin time, fibrinogen
Urinalysis:	pH, specific gravity, blood, glucose, protein, ketones
Pregnancy Test:	for women of childbearing potential only; serum at Screening, urine at each other visit.
Serology	Hepatitis B surface antigen, and hepatitis C

All blood samples for the clinical laboratory tests must be taken in a fasting state, at least 8 hours after the previous drug application.

Blood and urine samples for hematology, and serum chemistry will be sent to a central laboratory for analysis. Urine pregnancy tests and dipstick will be conducted at the study sites.

10.3.4.1.2 Specimen Handling Requirements

The transmission of infectious agents may occur through contact with contaminated needles and blood or blood products. Consequently, appropriate blood and body fluid precautions should be employed by all study personnel involved in the collection of blood and handling of specimens in both the clinic and laboratory settings. Refer to current recommendations of the appropriate authorities.

In addition to appropriate handling of subject samples, specific regulations exist regarding the shipment of biologic/etiologic samples. Procedures and regulations for the packaging and shipping of infectious samples are outlined in the study laboratory manual. The investigator is responsible for ensuring that all study samples that are to be transported to another location are packed and shipped appropriately according to the applicable regulations.

Samples for assessment of clinical laboratory tests will be transported to the Clinical Reference Laboratory (see the study laboratory manual for addresses).

10.3.4.1.3 Evaluation of Clinical Laboratory Values

The normal ranges of values for the clinical laboratory assessments in this study will be provided by the responsible laboratory and submitted to Mayne Pharma LLC prior to beginning the study. They will be regarded as the reference ranges on which decisions will be made.

If a laboratory value is out of the reference range, it is not necessarily clinically significant. The investigator must evaluate the out-of-range values and record his or her assessment of the clinical significance in the appropriate eCRF.

All clinical laboratory values that in the investigator's opinion show clinically significant or pathological changes during or after termination of treatment must be reported as AEs and followed, as described in Section 11.2.5.

All measurements described in this section are recognized standard methods.

10.3.4.2 Clinical Examinations

10.3.4.2.1 Vital Signs

Vital signs, including height and weight (only assessed at Screening), blood pressure, and pulse will be measured.

10.3.4.2.2 Twelve-lead Electrocardiogram

A standard 12-lead ECG will be performed after the subject has been supine for at least 5 minutes. All ECG recordings will be identified with the subject number, date, and time of the recording. Gel ECG electrodes may be used for ECGs because they are more conductive and cause less trauma on compromised skin. Efficacy assessments should be conducted before ECGs to avoid possible artefact/changes from the ECG.

For subjects in the PK substudy, additional ECGs will be performed postdose during serial blood sampling on Day 1 and Day 30.

If there is a marked prolongation of the QT/QTc interval during treatment, a subject should be discontinued from the IP but remain in the study until full resolution of the event. The DSMB will be informed immediately of such an occurrence.

10.3.4.2.3 Physical Examination

A complete physical examination excluding the genitourinary examination will be performed at Screening, while limited physical examinations (to include HEENT, cardiorespiratory, abdomen, and range of motion) will be performed as indicated in the Schedule of Events (Section 2.2).

10.3.4.2.4 Other Safety Variables

Local tolerability will be assessed on a 0-3 scale (none, mild, moderate, severe). All application site reactions will be recorded as TEAEs in the diary. These should include the date and severity of the TEAE.

10.3.4.3 Adverse Events

The definitions and management of AEs, and any special considerations for AEs, are provided in Section [11](#).

11. ADVERSE EVENTS

11.1. Definitions

11.1.1 Adverse Events

An AE is defined as any untoward medical occurrence in a patient or clinical investigation subject administered a pharmaceutical product that does not necessarily have a causal relationship with this treatment. An AE can therefore be any unfavorable and unintended sign (including an abnormal laboratory finding, for example), symptom, or disease temporally associated with the use of a medicinal product, whether or not related to the medicinal product.

Pre-existing diseases or conditions will not be considered AEs unless there is an increase in the frequency or severity, or a change in the quality, of the disease or condition. (Worsening of a pre-existing condition is considered an AE.)

Events that occur in subjects treated with control product are also considered AEs.

11.1.2 Adverse Drug Reaction

All noxious and unintended responses to an investigational product related to any dose should be considered adverse drug reactions (ADRs).

The phrase “responses to an investigational product” means that a causal relationship between an investigational product and an AE is at least a reasonable possibility, i.e., the relationship cannot be ruled out. All AEs judged by either the reporting investigator or the sponsor as having a reasonable causal relationship to an IP qualify as ADRs.

All AEs for which the judgment of relationship to IP is “possible” or higher will be considered ADRs. If a relationship to IP is not provided, then the AE must be treated as if it were “possible.”

11.1.3 Unexpected Adverse Event/Adverse Drug Reaction

An expected AE or ADR is one for which the nature or severity is consistent with the known AE profile of the product. For a preapproval test product, the known information is contained in the IB. For a marketed product, the known information is contained in the current package insert for the product.

An unexpected adverse event (UAE) or unexpected adverse drug reaction (UADR) is one for which the nature or severity of which is not consistent with the applicable product information (e.g., Investigator’s Brochure [IB] for an unapproved investigational product or package insert/summary of product characteristics for an approved product). For example, hepatic necrosis would be unexpected (greater severity) if the IB only listed elevated hepatic enzymes or hepatitis. Likewise, cerebral thromboembolism and cerebral vasculitis would be unexpected (greater specificity) if the IB only listed cerebral vascular accidents.

Furthermore, reports that add significant information on specificity or severity of a known, already documented adverse reaction constitute unexpected events.

11.1.4 Serious Adverse Events/Drug Reaction

A serious adverse event (SAE) is any untoward medical occurrence that at any dose:

- results in death
- is life-threatening
NOTE: The term “life-threatening” in the definition of “serious” refers to an event in which the subject was at risk of death at the time of the event; it does not refer to an event that hypothetically might have caused death if it were more severe.
- requires inpatient hospitalization or prolongation of existing hospitalization
NOTE: Inpatient hospitalization is defined as 24 hours in a hospital or an overnight stay. An elective hospital admission to treat a condition present before exposure to the IP, or a hospital admission for a diagnostic evaluation of an AE, does not qualify the condition or event as an SAE. Further, an overnight stay in the hospital that is only due to transportation, organization, or accommodation problems and without medical background does not need to be considered an SAE.
- results in persistent or significant disability/incapacity
- is a congenital anomaly
NOTE: A congenital anomaly in an infant born to a mother who was exposed to the IP during pregnancy is an SAE. However, a newly diagnosed pregnancy in a subject that has received an IP is not considered an SAE unless it is suspected that the IP(s) interacted with a contraceptive method and led to the pregnancy.
- is an important medical event
NOTE: Medical and scientific judgment should be exercised in deciding whether it is appropriate to consider other situations serious, such as important medical events that may not be immediately life-threatening or result in death or hospitalization but may jeopardize the subject or may require intervention to prevent one of the other outcomes listed in the definition above. Examples of such events are intensive treatment in an emergency room or at home for allergic bronchospasm, blood dyscrasias, or convulsions that do not result in hospitalization, development of drug dependency, or drug abuse. The occurrence of malignant tumors is also to be considered serious.

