11.2.6 Reporting

11.2.6.1 Serious Adverse Events

The investigator or designee must report all SAEs promptly to Premier Research within 24 hours of first becoming aware of the event by e.g., completing, signing and dating the Serious Adverse Event Report Form, verifying the accuracy of the information recorded in the form with the source documents and eCRF, and sending the SAE form to the Premier Research by one of the following methods:

Email: [contact]

Email: [contact]

[contact]

[contact]

This written report should be submitted on the SAE form provided for this purpose. At the time of first notification, the investigator or designee should provide the following information, if available:

- Protocol number
- Reporter (study site and investigator)
- Suspect IP
- Subject's study number
- Subject's year of birth
- Subject's gender
- Date of first dose of IP(s)
- Date of last dose of IP(s), if applicable
- Adverse event term
- Date of occurrence of the event
- A brief description of the event, outcome to date, and any actions taken
- The seriousness criteria(on) that were met
- Concomitant medication at onset of the event
- Relevant medical history information
- Relevant laboratory test findings
- Investigator's opinion of the relationship to IP(s) ("Is there a reasonable possibility that the IP caused the SAE? Yes or No?")
- Whether and when the investigator was unblinded as to the subject's treatment assignment

Any missing or additional relevant follow-up information concerning the SAE should be sent to the sponsor/sponsor representative via the same contact details above as soon as possible on a follow-up SAE Report Form, together with the following minimal information (initial report, adverse event, date of occurrence, subject identification (ID), study ID, IP, and site number); this will allow the follow-up information to be linked to the initial SAE report.

Specific information may be requested by the Premier Research Pharmacovigilance Department using a follow-up request form or via email communication.

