11.2.6.3 Nonserious Adverse Events

Nonserious AEs will be recorded in the eCRF and reported by Premier Research to Mayne Pharma LLC in aggregate monthly status reports.

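### The SAE definition exempts every admission for diagnostic work-up of an AE, planned or not, so some unplanned AE-driven inpatient stays lose SAE status

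*Protocol*

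**What the plan says.** Protocol Section 11.1.4 lists among the seriousness criteria an event that "requires inpatient hospitalization or prolongation of existing hospitalization". The note under it begins: "Inpatient hospitalization is defined as 24 hours in a hospital or an overnight stay". It then sets out three exemptions:

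- "An elective hospital admission to treat a condition present before exposure to the IP";
- "a hospital admission for a diagnostic evaluation of an AE, does not qualify the condition or event as an SAE";
- an overnight stay caused only by transport, organisational or accommodation problems, with no medical reason behind it.

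The last criterion in the section, the important medical event, is left to judgment: "Medical and scientific judgment should be exercised in deciding whether it is appropriate to consider other situations serious".

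Seriousness decides how an event is handled. Under Section 11.2.6.1 the site "must report all SAEs promptly to Premier Research within 24 hours of first becoming aware of the event". Under Section 11.2.6.3, "Nonserious AEs will be recorded in the eCRF and reported by Premier Research to Mayne Pharma LLC in aggregate monthly status reports". Section 11.2 has sites record nonserious AEs that start up to 14 days after the last day of participation, and SAEs that start up to 30 days after it. Section 13.1.6.2 gives SAEs their own summary and listing.

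**The concern.** The first and third exemptions remove stays that say nothing about the study drug: a planned admission for an earlier condition, or a night in hospital for logistical reasons. The second is different in kind. It removes stays that happen because of an AE, and nothing in the wording confines it to stays arranged in advance.

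Reported SAEs are a named safety endpoint in the synopsis, and safety is part of the primary objective (Section 6.1). The DSMB's review of Cohort A also settles whether adolescents may enrol (Section 12). If an event that put a subject in hospital unexpectedly is classed as nonserious because the stay was for investigation, the sponsor hears of it more slowly and the SAE summary omits it. An unplanned admission often starts as a work-up and turns into treatment. The note gives no rule for telling the two apart, so sites could classify similar events differently.

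**Working it through.** This is a check of the text; the protocol states no figure on the point to reproduce.

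**Step 1: which qualifiers belong to which exemption.** The elective qualifier and the requirement that the condition precede exposure both sit inside the first exemption ("An elective hospital admission to treat a condition present before exposure to the IP"). The diagnostic exemption ("a hospital admission for a diagnostic evaluation of an AE, does not qualify the condition or event as an SAE") carries no limit on planning, length of stay or time of onset. It names AEs, so it reaches events that arise on treatment.

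**Step 2: apply the section to one case.** Take an AE that starts on treatment and leads to an unplanned overnight stay for investigation only.

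| Text in Section 11.1.4 | Result for this case |
|---|---|
| Hospitalization criterion with its time definition | Met: overnight stay |
| Exemption for elective admission, earlier condition | Does not apply |
| Exemption for diagnostic evaluation of an AE | Applies: not an SAE |
| Exemption for logistical overnight stay | Does not apply: there is a medical reason |
| Death, life-threatening, disability, congenital anomaly | Not met, by assumption |
| Important medical event | Possible, if the investigator so judges |

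The third exemption removes only stays without a medical reason. This implies that stays with one are meant to count, which the second exemption then undoes for work-up admissions.

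**Step 3: follow the event if no other criterion is judged to apply.**

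| Aspect | If SAE | If nonserious |
|---|---|---|
| Reporting | Site to Premier Research within 24 hours of awareness (11.2.6.1) | Case report form, then aggregate monthly report to the sponsor (11.2.6.3) |
| Collection after last day of participation | 30 days (11.2) | 14 days (11.2) |
| Analysis | Separate SAE summary and listing (13.1.6.2) | General AE summaries only, unless it led to discontinuation |

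The difference in collection window is 30 − 14 = 16 days. An event of this kind that starts on days 15 to 30 need not be recorded at all once the note makes it nonserious.

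**Step 4: look for another mandatory route.** Section 11.2.6.2 requires immediate reporting of suspected serious adverse drug reactions, but the reaction must first be called serious. The important-medical-event criterion permits capture without requiring it. Neither restores mandatory SAE status.

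**Step 5: version.** The clause stands in the Amendment 1 text and in the same words in the original protocol. The amendment's table of changes lists no revision to it. The document also holds the closing sections of another version, whose Section 11 is not shown, so the wording there could not be checked.

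**The case against.** The strongest reply is that a note exists to narrow its criterion. Criterion and note are read together, and a site that follows the note is doing what the protocol says. That stands. A reader might infer that two rules of the protocol contradict each other, but this is one criterion with an exception drawn too widely.

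A reader might also infer that every unplanned stay caused by an AE loses SAE status. The text does not go that far: an admission to treat an AE still counts, so does prolongation of an existing stay, and the other criteria remain open. The important-medical-event criterion is a natural home for an AE that needs an inpatient work-up. It is discretionary, however, so it softens the gap without closing it.

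Nor do the documents support the inference that the DSMB would be left unaware. Marked QT/QTc prolongation goes to the DSMB immediately whatever its seriousness (Section 10.3.4.2.2). The DSMB reviews unblinded aggregate safety and tolerability data, including PK and ECG results, and not an SAE count alone (Section 12). Clinically significant changes in liver function tests must be reported as AEs (Section 10.3.4.1.3) and are a stopping rule (Section 9.4.1), so they would also appear among AEs leading to discontinuation. All of this stands. It shows that such events can be seen in the AE data; it does not put them back on the 24-hour route or into the SAE summary.

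Finally, one might want to express the effect as a change in the Cohort A SAE rate. The documents give no frequency for such admissions, so any rate would be an assumption and none is offered here.

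**Conclusion.** The point holds as an over-broad exemption. As written, an unplanned stay of 24 hours or overnight to investigate an on-treatment AE is not an SAE unless another criterion is judged to apply. For such an event, 24-hour reporting gives way to aggregate monthly reports, the collection window falls by 16 days, and the event leaves the separate SAE summary. If it starts within the 14-day window it is still recorded as an AE.

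This rests on reading the exemption literally and on no other seriousness criterion being applied. The number of events is unknown and may be small. No efficacy endpoint or sample size is touched, and Section 13.1.6 plans no formal inference on safety. The clause should be corrected because it affects the completeness and speed of SAE capture and costs little to change.

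**What to change.** In Section 11.1.4, delete the clause on admission for diagnostic evaluation of an AE, or limit it expressly to planned, elective diagnostic admissions. Add a sentence stating that an unplanned admission of 24 hours or overnight caused by an AE meets the hospitalization criterion. Keep the exemptions for elective admission for an earlier condition and for purely logistical overnight stays. Carry the same wording into the SAE completion guidance given to sites.

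The cost is one clause, one sentence and a guidance update, with possibly a few more expedited SAE reports.
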